8.1.1 DEFINITION OF ADVERSE EVENTS (AE)

An adverse event (AE) is defined as any untoward medical occurrence, including an exacerbation of a pre-existing condition, in a patient in a clinical investigation who received a pharmaceutical product. The event does not necessarily have to have a causal relation with this treatment.

8.1.2 DEFINITION OF SERIOUS ADVERSE EVENTS (SAE)

A serious adverse event (SAE) is defined as any AE that results in death, is immediately life-threatening, results in persistent or significant disability/incapacity, requires or prolongs patient hospitalization, is a congenital anomaly/birth defect, or is to be deemed serious for any other reason if it is an important medical event when based on appropriate medical judgement that may jeopardize the patient and may require medical or surgical intervention to prevent one of the other outcomes listed in the above definitions.

Patients may be hospitalized for administrative or social reasons during the study (e.g. long distance from home to site). These and other hospitalizations planned at the beginning of the study do not need to be reported as an SAE in case they have been reported at screening visit in the source data and have been performed as planned.

8.1.3 DEFINITION OF UNANTICIPATED PROBLEMS

Unanticipated adverse therapy effect, any serious adverse effect on health or safety, or any life-threatening problem or death caused by, or associated with, if that effect, problem, or death was not previously identified in nature, severity, or degree of incidence or any other unanticipated serious problem associated with the therapy that relates to the rights, safety, or welfare of subjects.

8.2 CLASSIFICATION OF AN ADVERSE EVENT

8.2.1 SEVERITY OF EVENT

All AEs will be graded using the CTCAE 5.0 criteria (Appendix 3). For AEs not included in the protocol-defined grading system, the following guidelines will be used to describe severity.

Mild – Events require minimal or no treatment and do not interfere with the participant's daily activities.

Moderate – Events result in a low level of inconvenience or concern with the therapeutic measures. Moderate events may cause some interference with functioning.

Severe – Events interrupt a participant’s usual daily activity and may require systemic drug therapy or other treatment. Severe events are usually potentially life-threatening or incapacitating.

8.2.2 RELATIONSHIP TO STUDY AGENT

For all collected AEs, the clinician who examines and evaluates the participant will determine the AE’s causality based on temporal relationship and his/her clinical judgment. The degree of certainty about causality will be graded using the categories below.

Related – The AE is known to occur with the study agent, there is a reasonable possibility that the study agent caused the AE, or there is a temporal relationship between the study agent and event. Reasonable possibility means that there is evidence to suggest a causal relationship between the study agent and the AE.

Not Related – There is not a reasonable possibility that the administration of the study agent caused the event, there is no temporal relationship between the study agent and event onset, or an alternate etiology has been established.

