and platelet-derived growth factor receptor β . In a randomized, double blind, placebo-controlled phase III trial (DECISION), Sorafenib also was associated with a significant increase in progression-free survival (10.8 versus 5.4 months) and response rate (54.1% vs. 33.8%) (10). Cabozantinib, inhibits the hepatocyte growth factor receptor (MET); the vascular endothelial growth factor receptor 2; and RET. In a phase III randomized placebo controlled study (EXAM), Cabozantinib improved the median progression-free survival from 4.0 to 11.2 months (hazard ratio, 0.28 [0.19 to 0.40]); as well as the response rate from 0% to 28% (11). Finally, Vandetanib selectively targets RET, VEGFR and EGFR signaling. In a phase III randomized, double-blind, placebo-controlled study (ZETA), Vandetanib showed to prolong the progression free survival from 19.3 months in the placebo group to 30.5 months in the Vandetanib group (hazard ratio, 0.46 [0.31-0.69]); and to improve the response rate (49% vs 13%) (12). Response to therapy was seen rapidly, at a median of 2 months for radiological response and even earlier for tumor markers in the SELECT study.(9) Most patients on TKI therapy, however, develop resistance to the drug after 12-18 months of treatment, and then tumor restarts progression.(9-12)

TKI therapy has proven to increase the progression free survival; however, their impact on overall survival is still unclear, in part due to the rapid development of tumor resistance. Furthermore, TKI treatment is associated to significant toxicity. Severe (grade 3-4) treatment related adverse events were reported in 76%, 69% and 37% of the patients treated with TKI on the SELECT, EXAM and DECISION studies, respectively, compared to 10%, 33% and 26% in their respective placebo-control groups (9-11). As a consequence of the adverse events, a dose reduction was necessary in 68% of the study participants treated with Lenvatinib, and treatment needed to be interrupted in 82% of patients in the SELECT study (9). Similarly, 64% of the patients required a dose reduction and 66% treatment interruption under Sorafenib treatment in the DECISION trial.(10) In the ZETA study, a significantly higher proportion of patients required dose reduction due to adverse events or QT prolongation in the Vandetanib group than in the placebo group (35% vs. 3%).(12) TKI treatment was permanently discontinued in around 15% of the participants in all studies due to adverse events (9-12).

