8. ASSESSMENT OF SAFETY

8.1 SPECIFICATION OF SAFETY PARAMETERS

Study participants will be monitored closely based on clinical, laboratory and imaging studies as outlined in study calendar (Table 8). Lenvatinib, Sorafenib, Cabozantinib and Vandetanib AEs and SAEs have been well described in literature (9-12). Patients will be educated and encouraged to report any AEs and SAEs promptly. Our primary endpoints include evaluation of safety and toxicity of adaptive TKI therapy and its comparison to conventional TKI therapy by measuring incidence of AEs and SAEs and time to its developments in adaptive and conventional therapy arms.

All AEs and SAEs will be graded according to CTCAE v5.0 (Appendix 3) and recorded in patient's charts and CRFs.

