8.4 REPORTING PROCEDURES

8.4.1 ADVERSE EVENT REPORTING

All AEs occurring prior to initiation of TKI therapy do not need to be reported.

All AEs occurring after first administration of TKI therapy (Lenvatinib, Sorafenib, Cabozantinib, or Vandetanib) and 30 days after last administration of TKIs will be considered as on treatment. All AEs will be collected and graded according to CTCAE v5.0 (Appendix 3), with the exception of Grade 1 laboratory abnormalities which will not be collected. All Grade 2 and above toxicities will be collected and documented by the investigator, but only Grade 3 toxicities deemed possibly, probably or definitely related to the study treatment will be reported on the appropriate CRFs/SAE reporting forms. Only SAEs will be reported to the PI. All AEs, including those persisting after end of study treatment must be followed up until they have resolved or have been sufficiently characterized or the principal investigator decides to not further pursue them.

Serious and non-serious AEs occurring later than 30 days after last administration of trial drugs will only be reported in case they are considered drug-related or trial (procedure) related.

Deaths (unless they are considered drug-related or trial related) will not be reported as SAE when they occur later than 30 days after last administration of the trial.

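### The related-only CRF rule in Section 8.4.1 conflicts with Sections 8.1 and 8.3 and, if followed, would tend to under-count background Grade 3 events during adaptive-arm TKI breaks

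*Combined protocol and SAP*

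**What the plan says.** Section 8.2.2 uses a two-level causality scale. An event is related if any one of several conditions holds. One is "The AE is known to occur with the study agent"; another is "or there is a temporal relationship between the study agent and event". It is not related if there is no reasonable possibility of causation, if there is no temporal relationship, "or an alternate etiology has been established".

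Section 8.4.1 has the investigator collect and document toxicities of Grade 2 and above, but "only Grade 3 toxicities deemed possibly, probably or definitely related to the study treatment will be reported on the appropriate CRFs/SAE reporting forms". It treats the 30 days after last administration as on treatment. After that, AEs are reported only if drug- or trial-related.

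Two sections set no such filter. Section 8.1 states: "All AEs and SAEs will be graded according to CTCAE v5.0 (Appendix 3) and recorded in patient's charts and CRFs". Section 8.3 has AEs documented whatever their relationship to drug, without naming the form. Section 8.4.2 records all SAEs in the trial database, and puts deaths and immediately life-threatening events on the SAE form whether or not they are related.

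Section 8.1 describes the use of these data as evaluating adaptive therapy and "its comparison to conventional TKI therapy by measuring incidence of AEs and SAEs and time to its developments" in the two arms. It counts this among the primary endpoints, although Section 4.2.1 names only time to discontinuation.

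**The concern.** Dosing time differs between the arms by design. Conventional patients take TKI daily (Section 4.1). Adaptive patients have it withheld while the marker stays below 70% of baseline (Table 8, footnote a). Staff are unblinded at assignment (Section 10.5.1), so the person judging causality knows who is on a break.

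A recording filter that depends partly on whether the patient is currently dosed therefore acts differently in the two arms. A severe event from the disease or an intercurrent illness can pass the temporal limb in a patient taking TKI every day and fail it in a patient who is weeks into a break. Fewer truly drug-caused events during breaks would be a real benefit of the strategy. The problem is confined to background events, whose loss would look like the same benefit. Section 4.2.1 expects less drug-associated toxicity in the adaptive arm, so the harm comparison bears on half of the hypothesis.

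**Working it through.** **No plan figure to reproduce.** The plan gives no number for the harm comparison, and Section 10 contains no AE analysis. The 82% power in Section 10.1 concerns time to discontinuation and does not enter this point.

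**Which rule sends what to the CRF.** Under Section 8.1, every AE goes to the CRF. Under Section 8.4.1, only related Grade 3 toxicities do. Both cannot hold, and no precedence is stated. Section 8.4.2 takes SAEs, deaths and life-threatening events out of the filter. Grade 4 means life-threatening and Grade 3 includes events where hospitalization is indicated (Appendix 3), while hospitalization makes an event serious (Section 8.1.2). What remains exposed to the filter is mainly non-serious Grade 3 events.

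**Whether the 30-day rule can differ by arm.** Section 6.1.8 caps delays for toxicity or palliative treatment at 4 weeks, so a conventional patient still on protocol therapy should not pass 30 days off drug. An adaptive patient can, since breaks are reviewed about every 28 days (Section 7.3.3) and may run over several reviews. Section 8.4.1 does not say whether last administration means the last dose before a break or the final dose. If the window restarts at each break and is enough for attribution, the share of a break left outside it is (length − 30)/length:
- 28 days: none
- 56 days: 26/56 = 46%
- 84 days: 54/84 = 64%

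**Size, as an illustration only.** Assume the same true background rate in both arms, and that every on-TKI background event is called related. Let f be the share of adaptive-arm time that is off TKI and outside any window that alone secures attribution. Let c be the chance that an event in that time is still called related. The documents give neither.

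Counted rate ratio, adaptive to conventional = (1 − f) + f·c = 1 − f(1 − c).

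| f | c = 0 | c = 0.5 | c = 1 |
|---|---|---|---|
| 0.2 | 0.80 | 0.90 | 1.00 |
| 0.4 | 0.60 | 0.80 | 1.00 |
| 0.6 | 0.40 | 0.70 | 1.00 |

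For example, f = 0.4 and c = 0.5 gives 1 − 0.4 × 0.5 = 0.80.

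If only a share k of on-TKI background events is called related, because another cause is established for the rest, the ratio becomes 1 − f(1 − c/k). The deficit is then f(k − c) times the background rate. It shrinks as k falls toward c and vanishes when attribution is equally likely on and off drug.

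With all such events entered regardless of attribution over the same window, the ratio is 1.00 for any f.

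**The case against.** The strongest reply is that Section 8.1 already compares AEs and SAEs with no relatedness limit and already sends all of them to the CRF, so no related-only comparison is specified anywhere. As a reading of Section 8.1 this is right. A reader might infer that harms reach the CRF only if judged drug-related; the documents do not support that, since Sections 8.1, 8.3 and 8.4.2 say otherwise. But staff who follow Section 8.4.1 would not enter the data that Section 8.1 needs, so the conflict still matters.

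A reader might also infer that the conventional arm loses no events, that breaks lose all of them, and that the net effect always favours the adaptive arm. None of these follows. An established alternate cause can make an on-TKI event not related, though this overlaps the temporal limb with no stated precedence. The known-effect limb has no timing condition, so it can cover typical TKI toxicities during a break. The 30-day window may cover short breaks entirely. Vandetanib's 19-day half-life (Section 6.1.8.2) extends a plausible temporal link. Detection may run the other way: Table 8 schedules clinical assessments such as the physical examination every 3 cycles on conventional therapy but every cycle off TKI, although Section 7.3.3 differs.

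Finally, it is tempting to take background risk from Section 2.1, where severe events were 76%, 69% and 37% on TKI, "compared to 10%, 33% and 26% in their respective placebo-control groups", and to turn the bias into percentage points. Those placebo figures are described as treatment-related, so they have already passed an attribution judgment. Median progression-free survival in the same three trials was 18.3 versus 3.6, 11.2 versus 4.0 and 10.8 versus 5.4 months, so the active and placebo percentages may cover very different exposure times. Off-TKI time is not given at all. A percentage-point estimate would be unsupported.

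**Conclusion.** The point holds in a limited form. The recording rules conflict. If Section 8.4.1 is applied as written, attribution by timing would tend to drop background events, mainly non-serious Grade 3 and mainly in longer breaks, from the adaptive arm while similar events stay counted in the conventional arm. The bias from this filter is toward the adaptive arm.

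Its size cannot be derived from the documents. The ratios of 0.80 to 0.40 (no off-TKI event attributed) and 0.90 to 0.70 (half attributed) rest on an assumed 20% to 60% of adaptive-arm time being off TKI and outside any attribution window, equal true background rates, and full attribution on TKI. With breaks of about 28 days and a window that restarts at each break, the effect could be negligible. It concerns the harm comparison in Section 8.1, not the power calculation.

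**What to change.** Reconcile Sections 8.1, 8.3, 8.4.1 and 8.4.2 so that all Grade 3 or higher AEs and all SAEs are entered on the CRF regardless of attribution, in both arms, over the same window from randomization. State how last administration is read when TKI is withheld in a planned break, so that the 30-day clause does not shorten that window in one arm. State in Section 8.1 that the between-arm harm comparison, for both incidence and time to onset, is all-cause, and keep the drug-related subset as a supportive table.

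The cost is protocol wording and some extra CRF entries; Section 8.4.1 already has the investigator collect and document these events. All-cause counts include events unrelated to drug and so dilute a true difference slightly, which the supportive table helps to show.

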8.2.3 EXPECTEDNESS

The PI will be responsible for determining whether an AE is expected or unexpected. An AE will be considered unexpected if the nature, severity, or frequency of the event is not consistent with the risk information previously described for the study agent.

8.3 TIME PERIOD AND FREQUENCY FOR EVENT ASSESSMENT AND FOLLOW-UP

The study participants will be monitored closely throughout the study for occurrence of AE or SAE. The patients will be educated regarding most common AEs and SAEs and will be encouraged to report promptly.

If AEs and SAEs occur, information to be collected includes event description, time of onset, clinician’s assessment of severity, relationship to study product, and time of resolution/stabilization of event. All AEs occurring during the study will be documented appropriately, regardless of relationship. All AEs will be followed to adequate resolution. Any medical condition that is present at the time that the participant is screened will be considered as baseline and not reported as an AE. However, if the study participant’s condition deteriorates at any time during the study, it will be recorded as an AE. Unanticipated problems will be recorded in the data collection system throughout the study.

Events will be followed for outcome information until resolution or stabilization is achieved.

8.4 REPORTING PROCEDURES

8.4.1 ADVERSE EVENT REPORTING

All AEs occurring prior to initiation of TKI therapy do not need to be reported.

All AEs occurring after first administration of TKI therapy (Lenvatinib, Sorafenib, Cabozantinib, or Vandetanib) and 30 days after last administration of TKIs will be considered as on treatment. All AEs will be collected and graded according to CTCAE v5.0 (Appendix 3), with the exception of Grade 1 laboratory abnormalities which will not be collected. All Grade 2 and above toxicities will be collected and documented by the investigator, but only Grade 3 toxicities deemed possibly, probably or definitely related to the study treatment will be reported on the appropriate CRFs/SAE reporting forms. Only SAEs will be reported to the PI. All AEs, including those persisting after end of study treatment must be followed up until they have resolved or have been sufficiently characterized or the principal investigator decides to not further pursue them.

Serious and non-serious AEs occurring later than 30 days after last administration of trial drugs will only be reported in case they are considered drug-related or trial (procedure) related.

Deaths (unless they are considered drug-related or trial related) will not be reported as SAE when they occur later than 30 days after last administration of the trial.

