4.2 STUDY ENDPOINTS

4.2.1 PRIMARY ENDPOINT

The primary endpoint is time to TKI treatment discontinuation due to progressive disease, intolerability (Grade 3 and 4 toxicities refractory to best symptom management that are deemed probably or definitely related to study treatment only), or disease-related death at 2 years. We hypothesize that time on TKI treatment will be significantly longer for patients on the adaptive therapy arm than on the conventional therapy arm because we expect a decrease in drug-associated toxicities and a delay in the selection of resistant clones in the adaptive therapy arm.

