6.1.8.2 MANAGEMENT OF MOST COMMON SIDE EFFECTS SPECIFIC TO EACH TKI AGENT

Dose Reduction and Interruption Instructions for Lenvatinib

Table 1. Adverse Reactions Requiring Dose Modification of Lenvatinib

Adverse Reaction	CTCAE Grade	Action	Dose Reduce and Resume Lenvatinib
Hypertension	Grade 3 ¹	Hold	Resolves to Grade 0, 1, or 2
	Grade 4	Discontinue	Do Not Resume
Cardiac Dysfunction	Grade 3	Hold	Resolves to Grade 0, 1, or baseline
	Grade 4	Discontinue	Do Not Resume
Arterial Thrombotic Event	Any Grade	Discontinue	Do Not Resume
Hepatotoxicity	Grade 3 or 4	Hold OR Discontinue	Consider resuming at reduced dose if resolves to Grade 0-1 or baseline
Hepatic Failure	Grade 3 or 4	Discontinue	Do Not Resume
Proteinuria	Greater than or equal to 2 gm/24 hours	Hold	Resolves to less than 2 gm/24 hours
Nephrotic Syndrome	-----	Discontinue	Do Not Resume
Nausea, Vomiting, and Diarrhea ²	Grade 3	Hold	Resolves to Grade 0, 1, or baseline
Vomiting and Diarrhea ²	Grade 4	Discontinue	Do Not Resume
Renal Failure or Impairment	Grade 3 or 4	Hold OR Discontinue	Consider resuming at reduced dose if resolves to Grade 0-1 or baseline
GI Perforation	Any Grade	Discontinue	Do Not Resume
Fistula	Grade 3 or 4	Discontinue	Do Not Resume
QTc Prolongation	Greater than 500 ms	Hold	Resolves to less than 480 ms or baseline
Reversible Posterior Leukoencephalopathy syndrome	Any Grade	Hold OR Discontinue	Consider resuming at reduced dose if resolves to Grade 0 to 1
Hemorrhage	Grade 3	Hold	Resolves to Grade 0 to 1
	Grade 4	Discontinue	Do Not Resume

1: Grade 3 despite optimal anti-hypertensive therapy

2: Initiate prompt medical management for nausea, vomiting or diarrhea. Permanently discontinue for Grade 4 vomiting and diarrhea despite medical management

Other adverse reactions with Lenvatinib will be managed following the instructions from Table 2:

Table 2. Dose Modifications for Lenvatinib for treatment-related Persistent and Intolerable Grade 2 or Grade 3 Adverse Reactions or Grade 4 Laboratory Abnormalities^a

Adverse Reaction	Modification	Adjusted Dose ^b
First occurrence	Interrupt until resolved to Grade 0-1 or baseline	20 mg (two 10 mg capsules) orally once daily
Second occurrence ^c	Interrupt until resolved to Grade 0-1 or baseline	14 mg (one 10 mg capsule plus one 4 mg capsule) orally once daily

Third occurrence ^c	Interrupt until resolved to Grade 0-1 or baseline	10 mg (one 10 mg capsule) orally once daily
-------------------------------	---	---

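### Section 8.4.1 sends only related Grade 3 toxicities to the CRF, which conflicts with 8.1, 8.4.2 and the Grade 3 and 4 definition in 4.2.1 and leaves the tolerability comparison incomplete

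*Combined protocol and SAP*

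**What the plan says.** Section 8.4.1 separates collection from reporting within one sentence. For collection it says "All Grade 2 and above toxicities will be collected and documented by the investigator". For the forms it continues "but only Grade 3 toxicities deemed possibly, probably or definitely related to the study treatment will be reported on the appropriate CRFs/SAE reporting forms".

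Three other sections bear on the same events:

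- Section 8.1 sets no limit by grade or cause: "All AEs and SAEs will be graded according to CTCAE v5.0 (Appendix 3) and recorded in patient's charts and CRFs". It also describes, as part of the primary endpoints, a comparison made by "measuring incidence of AEs and SAEs and time to its developments in adaptive and conventional therapy arms".
- Section 8.4.2 sends deaths and immediately life-threatening events to the SAE Form whether or not they are attributed to treatment, and has all SAEs recorded in the OnCore database.
- Section 4.2.1 defines the intolerability component of the primary endpoint as "Grade 3 and 4 toxicities refractory to best symptom management that are deemed probably or definitely related to study treatment only".

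On causality, Section 8.2.2 gives the examining clinician two categories, related and not related. Sections 4.2.1 and 8.4.1 both rely on a finer scale (possibly, probably, definitely) that Section 8.2.2 does not define.

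**The concern.** The reporting clause names one grade. The collection clause just before it extends to higher grades, so the missing extension cannot simply be read in. Taken literally, the clause keeps Grade 4 off the CRF, along with every Grade 3 event judged unrelated. Because it covers the SAE reporting forms as well as the CRFs, it also collides with Section 8.4.2.

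What is at stake is the tolerability half of the primary objective. The trial expects adaptive dosing to reduce toxicity, and Section 8.1 proposes to show this by comparing AE incidence and timing between arms. A CRF holding only related Grade 3 events cannot support that comparison.

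The relatedness filter is a further weakness. Under Section 8.2.2 the examining clinician judges causality. Section 10.5.1 says that the consenting researchers learn the assignment, and no masking of AE assessors is described anywhere. Patients in the adaptive arm spend periods off drug, when a clinician may be less inclined to attribute an event to treatment. If attribution decides whether an event is entered at all, a difference between arms in how it is judged could not be examined afterwards from the CRF.

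**Working it through.** No arithmetic applies, so the check sets the rules side by side for each type of on-treatment event.

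| Event | Section 8.1 | Section 8.4.1, read literally | Other route in the plan |
|---|---|---|---|
| Death | CRF | Not named | SAE Form, any cause (8.4.2) |
| Grade 4, immediately life-threatening or otherwise serious | CRF | Not named | SAE Form if immediately life-threatening; OnCore as an SAE (8.4.2) |
| Grade 4, not serious | CRF | Not named | Investigator documentation (8.3, 8.4.1) and Power Chart (14.1); no CRF route |
| Grade 3, related | CRF | Reported | None needed |
| Grade 3, unrelated, serious | CRF | Excluded | OnCore as an SAE (8.4.2) |
| Grade 3, unrelated, not serious | CRF | Excluded | Investigator documentation and Power Chart; no CRF route |
| Grade 2 | CRF | Excluded | Investigator documentation and Power Chart; no CRF route unless serious |
| Date and reason for stopping | Not addressed | Not addressed | CRF (5.4.1 and Section 9) |

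1. **Do the rules agree?** No. Sections 8.1 and 8.4.1 give the same answer only for related Grade 3 events.

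2. **Is non-serious Grade 4 toxicity a real category in this plan?** Yes. The title of Table 2 in Section 6.1.8.2 covers "Persistent and Intolerable Grade 2 or Grade 3 Adverse Reactions or Grade 4 Laboratory Abnormalities" for lenvatinib, and the cabozantinib instructions have a category for Grade 4 hematologic reactions. Table 2 is a dose-modification rule, not a forecast of frequency. It does show that such events are foreseen and are handled by interruption and a lower dose. Under the SAE definition in Section 8.1.2, a laboratory abnormality of this kind need not qualify as serious.

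3. **Does the relatedness filter remove events that the primary endpoint needs?** Not at Grade 3. Section 8.4.1 admits possibly, probably and definitely related events, whereas Section 4.2.1 counts only probably and definitely related ones. The reporting filter is the wider of the two, so every Grade 3 event that qualifies under 4.2.1 passes it. The mismatch with 4.2.1 is confined to Grade 4.

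4. **Is a discontinuation for Grade 4 toxicity lost?** No. Its date and reason must be on the CRF under 5.4.1 and Section 9. For a non-serious Grade 4 event, what 8.4.1 does not supply is the grade and attribution as coded data, which are needed to confirm that the stop met 4.2.1.

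5. **Can the attribution terms be applied?** Not from the scale as defined. A two-category judgement under 8.2.2 cannot separate possibly from probably related, yet 4.2.1 depends on that distinction.

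**The case against.** The strongest reply is that this is a slip for Grade 3 and above, with little consequence. Section 4.2.1 names Grade 3 and 4 together, and the collection clause already extends upward. Fatal and immediately life-threatening events go to the SAE Form regardless of cause, and Appendix 3 describes Grade 4 in terms of life-threatening consequences. Section 8.3 has all AEs documented regardless of relationship, with severity and causality. Section 14.1 puts AE and laboratory data into an electronic system from which a laboratory grade could be derived. Section 8.5 has the monitoring committee reviewing all adverse events.

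Much of this stands, and it rules out three stronger readings that a reader might infer:

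- **That Grade 5 events, or Grade 4 events in general, go unrecorded.** Section 8.4.2 captures deaths and serious events.
- **That primary-endpoint events would be missed.** The date and reason for stopping are on the CRF.
- **That the severe-event rates of 37% to 76% in Section 2.1 measure the gap.** They combine Grade 3 and Grade 4 treatment-related events, and related Grade 3 is exactly what 8.4.1 does report.

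The reply does not remove the inconsistency. Section 8.3 does not name the CRF, and Section 14.1 does not identify its system as the CRF. Even if Grade 3 and above was intended, the conflict with 8.1 and the relatedness filter would remain.

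**Conclusion.** The point holds as an internal inconsistency that should be corrected. Its effect falls on the tolerability comparison by arm, not on the count of primary-endpoint events. Under 8.4.1 as written, non-serious Grade 4 toxicity and non-serious unrelated Grade 3 toxicity have no CRF route. The CRF would also lack the structured grade and attribution needed to verify that a non-serious Grade 4 stop met 4.2.1.

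The size cannot be put as a number. The documents do not give the Grade 4 share of toxicity, nor the share of Grade 3 events likely to be judged unrelated.

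The conclusion rests on two assumptions: that 8.4.1 is applied as worded, and that the tolerability analysis is run from the CRF. If staff follow 8.1 instead, the data would be complete, but the protocol does not say which section governs. Differential attribution between arms is a possibility that the open design allows; nothing in the documents shows that it will occur.

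**What to change.** - In 8.4.1, replace the reporting clause with Grade 3 or higher, entered on the CRF regardless of attribution, with grade and attribution as coded fields. State the SAE Form rule separately, so that 8.4.1 no longer appears to restrict 8.4.2.
- Reconcile 8.1 with 8.4.1 and 8.4.2. If lower grades are not to be entered on the CRF, 8.1 should say so and limit the comparison by arm to the grades that are.
- Use one causality scale in 8.2.2, 4.2.1 and 8.4.1, so that the attribution condition in the primary endpoint can be read directly from the recorded field.

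The cost is a protocol wording change and a modest increase in CRF entries. The investigator already documents Grade 2 and above, so no new assessment of patients is needed. The change affects data capture only.
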